4.6 Randomization

The randomization module is built into the electronic case report form (eCRF) system. When a patient is eligible for randomization, the study personnel clicks the randomization button in the eCRF system and receives a subject specific randomization ID, and the identification number of the IMP that should be dispensed to the subject.

An adaptive randomization method is used, meaning when a new subject is to be randomized, the treatment allocations of the previously entered subjects affect the allocation probability of the new subject.

Randomization is stratified for the factors listed in Table 3.

Table 3. Stratification factors in the randomization.

Variable	Levels
Location	- Colon
	- Rectum
Stage	-1
	- II
	- 111
Mutation type	- PIK3CA exons 9/20
	- PIK3CA (other exons)/PIK3R1/PTEN

The first subject in a specified stratum is allocated to the ASA or placebo arm with equal probability (0.5). A succeeding subject in a specified stratum is allocated with probability 1 to the treatment arm that has the smallest number of allocated subjects within the same stratum. If the two arms in a specified stratum have equal number of subjects the next subject in that stratum is allocated to the ASA or placebo arm with equal probability (0.5).

It is impossible for the principal investigator (PI) or study personnel to predict the allocation of the next subject in a specified stratum, since neither the subject specific randomization ID generated by the eCRF, nor the identification number of the IMP, contain information on which arm the subject was randomized to. In addition, there is no stratification by site, so the next randomized subject is likely to be at another site, giving even more protection against any theoretical possibility to deduce randomization order. The PI or study personnel do not have access to any subject list specifying randomization arm.

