8.1 Primary efficacy analysis

The analysis of the primary endpoint TTR assessed at 3 years from randomization in subjects with somatic alterations in the PIK3CA gene (exons 9/20) will be performed on a subset of the FAP containing only subjects with such somatic alterations.

The primary efficacy analysis will consist of a Cox proportional hazards model (PHM), including the covariate *Treatment* (ASA vs Placebo, defined by randomization). The baseline hazard will be stratified by the covariates used in the randomization – location (colon/rectum), and stage (I/II/III, included as a categorical variable). The strata will thus be the following

- Stratum 1: Colon, Stage II
- Stratum 2: Colon, Stage III,
- Stratum 3: Rectum, Stage I,
- Stratum 4: Rectum, Stage II,
- Stratum 5: Rectum, Stage III.

The Breslow method will be used to handle tied event-times. The model is given by

$$h_i(t) = h_{0,i}(t) \cdot \exp(\beta_{Treat} \cdot Arm),$$

where $h_j(t)$ and $h_{0,j}(t)$ denote the hazard function and baseline hazard function, respectively, for stratum j, j=1,...,5, and Arm denotes randomized arm (ASA=1, Placebo=0).

A HR=exp(β_{Treat}) comparing the hazard rates of the ASA and placebo arms will be estimated, along with a two-sided 95 % CI, and a two-sided p-value for testing the null hypothesis

 H_0 : $\beta_{Treat} = 0$

against the alternative hypothesis

 H_1 : $\beta_{Treat} \neq 0$.

The proportional hazards assumption (PHA) of the Treatment variable will be assessed using the Grambsch-Therneau test with a significance level of 5 %. If the PHA is violated, the overall HR will still be reported as the primary efficacy estimate, but an additional analysis will be added where follow-up is divided into two intervals, 0-1.5 years, and 1.5-3 years from randomization, and one HR for Treatment will be estimated for each time interval by adding an interaction term between Treatment and the time intervals.

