8.3 Exploratory analyses

In addition to the primary efficacy analysis and the analyses of secondary endpoints, some or all of the exploratory analyses listed in Table 10 (3-year endpoints) and Table 11 (5-year endpoints) may also be performed. All exploratory endpoints on the FAP will be analyzed as described in Section 8.1, however, for analyses in only colon/rectum/left-sided/right-sided colon subjects, the strata will only be defined by stage. For analyses with subgroups based on adjuvant treatment, an interaction-term between randomization arm and a time-varying treatment indicator will be used considering that adjuvant treatment for some subjects starts post-randomization. In result tables for exploratory analyses, 95 % Cl's, unadjusted for multiple testing will be presented, but not p-values.

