For the analyses on the PP3 and PP5 populations, stabilized inverse probability of treatment weights (IPTW) will be used to estimate the effect on the randomized population. The stabilized IPTW for each subject in the PP3 and PP5 populations will be calculated as the ratio between the probability of receiving the treatment that was received (ASA or Placebo) estimated from a logistic regression model without covariates, and the probability of receiving the treatment that was received (ASA or Placebo) estimated in a logistic regression model including the covariates age, sex, country, BMI, tumor location (colon/rectum), type of neoadjuvant treatment, ASA score, time from surgery until randomization, calendar time of randomization, platelet count at baseline, CEA at baseline, MSI status, BRAF V600E status, KRAS status, and tumor differentiation. The use of inverse probability of censoring weights (IPCW), in addition to the IPTW's, for the PP analyses has been considered, but deemed unsuitable for the ALASCCA trial data for several reasons: 1) The time-point for which a subject is to be considered non-compliant is not well-defined, and therefore an IPCW approach would demand strong assumptions and/or looking into the future for certain subjects, 2) Compliance (described in Section 4.8.2) is defined as a weighted average of the visit-specific compliance measurements over the whole study period, and censoring at the first visit-specific non-compliance would result in the censoring of a substantial number of subjects with an overall compliance of >80%, and 3) There are no relevant time-dependent covariates measured during follow-up to be included for capturing treatment-confounder feedback. Given the above considerations, the limitations of the suggested PP analysis approach must be highlighted when presenting the trial results.

A secondary or exploratory analysis involving the Mutation B subgroup may be subjected to sensitivity analysis to assess the impact of observations that may not represent true driver (cancer-relevant) variants. This may include repeating the analysis using a subset containing only high-confidence driver variants.

Table 10. Specification of variables and populations for the exploratory analyses in the ALASCCA trial for 3-year endpoints. Mutation A: PIK3CA exon 9 and 20 hotspot small mutations,

Mutation B: other PIK3CA, PIK3R1 and PTEN non-silent small mutations and focal/homozygous deletion of PTEN.

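### The per-protocol weights leave out tumour stage and the per-protocol outcome model is not stated, so the SAP specifies no control for stage in PP3 and PP5

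*SAP*

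**What the plan says.** - **Weights.** SAP 8.3 applies stabilised weights to PP3 and PP5 that "will be used to estimate the effect on the randomized population". The denominator model contains "the covariates age, sex, country, BMI, tumor location (colon/rectum), type of neoadjuvant treatment, ASA score, time from surgery until randomization, calendar time of randomization", followed by "platelet count at baseline, CEA at baseline, MSI status, BRAF V600E status, KRAS status, and tumor differentiation".
- **Scope of the stratified model.** Earlier in the same section: "All exploratory endpoints on the FAP will be analyzed as described in Section 8.1". The PP paragraph then describes the weights only and names no outcome model, strata or adjustment terms.
- **Primary model.** SAP 8.1 states: "The baseline hazard will be stratified by the covariates used in the randomization", namely "location (colon/rectum), and stage (I/II/III, included as a categorical variable", which gives five location-by-stage strata. It is defined on a "subset of the FAP containing only subjects with such somatic alterations".
- **Randomisation.** SAP 4.6: "Randomization is stratified for the factors listed in Table 3". Table 3 lists location, stage and mutation type.
- **Completeness.** SAP 5.4 notes that the randomisation factors must be in the eCRF before a subject can be randomised, so stage cannot be missing.
- **PP membership.** SAP 5.2.2 requires at least 80% compliance and full eligibility. It excludes, among others, subjects who leave because of an AE or SAE, for other medical reasons or by their own wish.

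**The concern.** Randomisation stratified by stage balances stage in the FAP. PP3 and PP5 are selected on what happens after randomisation, so that balance is no longer guaranteed. The weights are meant to recover the randomised population, yet they omit a strongly prognostic factor. The SAP itself treats stage as prognostic: the 18% planning rate in 4.5.2 is built from stage- and risk-factor-specific estimates.

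The omission looks unintended. SAP 8.3 keeps stage as the stratifier even in the single-location subgroups, and it explains at length why censoring weights were rejected, but gives no reason for leaving stage out. Location is also a stratum and was still put in the weights, so leaving stage to the strata is not an obvious explanation. CEA, differentiation and type of neoadjuvant treatment are at best weak proxies.

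What is at stake is how the PP hazard ratios are read against the FAP ones. The template for exploratory results (SAP Table 17) consists of two PP3 rows, and Protocol 10.13.6 says analyses are done on both FAP and PP.

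**Working it through.** **1. Text check.** The first part of the covariate list has 9 entries and the second has 6, so 9 + 6 = 15. Location is one of them; neither stage nor pTNM is.

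**2. Planning figures used for scale (SAP 4.5.2).** p1 = 0.18, p2 = 0.18 × 0.38 = 0.0684, mean 0.1242, two-sided 5%, 80% power, pooled test of two proportions:

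n = [1.96·√(2 × 0.1242 × 0.8758) + 0.8416·√(0.18 × 0.82 + 0.0684 × 0.9316)]² / 0.1116² ≈ 136 per arm, and 136/0.90 = 151.1, so 152. The SAP gives 135 and 150, which agrees closely enough. The concern does not rest on these figures.

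**3. Assumptions.** The documents give no stage mix, stage hazard ratios or PP retention. Assumed here: stage I/II/III 12/44/44%; 18% three-year recurrence on placebo; constant hazards; stage I vs II hazard ratio 0.5; stage III vs II hazard ratio 2, 3 or 5; 85% of stages I and II kept in PP in both arms. Only stage III retention r differs by arm.

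**4. Stage III share in PP** = 0.44r / (0.56 × 0.85 + 0.44r):

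- r = 0.75: 0.330/0.806 = 0.409
- r = 0.85: 0.374/0.850 = 0.440
- r = 0.70: 0.308/0.784 = 0.393
- r = 0.90: 0.396/0.872 = 0.454

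**5. Stage-specific recurrence that averages to 18%.** For a III vs II hazard ratio of 3 this is 5.5%, 10.7% and 28.7%. Check: 0.12 × 0.055 + 0.44 × 0.107 + 0.44 × 0.287 = 0.180.

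**6. Large-sample Cox hazard ratio when the true value is 1**

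| Stage III kept, ASA / placebo | III vs II = 2 | 3 | 5 | Stratified by stage |
|---|---|---|---|---|
| 80% / 80% | 1.000 | 1.000 | 1.000 | 1.000 |
| 75% / 85% | 0.975 | 0.964 | 0.952 | 1.000 |
| 70% / 90% | 0.951 | 0.929 | 0.906 | 1.000 |
| 85% / 75% | 1.025 | 1.037 | 1.050 | 1.000 |

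At a true value of 1, swapping the arms inverts the ratio, so 90% / 70% would give 1/0.951 = 1.05 to 1/0.906 = 1.10.

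**7. Do the weights as listed help, and does the fix work?** Simulation of 200,000 subjects, true hazard ratio 1, III vs II hazard ratio 3, stage III kept 75% vs 85%. The weights used location and a CEA-like proxy for stage, not all 15 covariates.

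| Analysis | Hazard ratio |
|---|---|
| PP, unweighted | 0.971 |
| PP, weights without stage, unstratified | 0.974 |
| PP, weights with stage, unstratified | 1.006 |
| PP, weights without stage, 8.1 strata | 1.007 |
| All randomised subjects | 1.008 |

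The weights without stage barely move the estimate. Either remedy brings it back to the value for all randomised subjects.

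**8. Scale against precision.** With 135 per arm and 18% in both arms there are 2 × 135 × 0.18 = 48.6 events. The standard error of the log hazard ratio is about 2/√48.6 = 0.287, so the 95% interval runs a factor exp(1.96 × 0.287) = 1.75 either way. Shifts to 0.975 and 0.906 are 0.025/0.287 = 0.09 and 0.099/0.287 = 0.34 standard errors.

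**9. A smaller, separate effect.** With a true stage-specific hazard ratio of 0.5 and equal retention (80% / 80%), the unstratified ratio is 0.504 to 0.515 and the stratified one 0.500. This is non-collapsibility, not bias from exclusions, but it means that an unstratified PP ratio and a stratified FAP ratio are not quite the same quantity.

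**The case against.** **The PP hazard ratios might be read as unstratified.** The SAP does not say so. It is silent on the PP outcome model, and an analyst could carry over the 8.1 strata, citing the remark in SAP 5.4 that endpoint analyses adjust for the randomisation factors. Step 7 shows that those strata alone would suffice. This stands, and it limits the point to what is specified. The remark does not settle the matter, however: it sits in the missing-data section, does not mention PP, and says that only randomisation factors are adjusted for, which does not fit weights with many other covariates.

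**Chemotherapy pauses might be thought to push stage III subjects out of PP.** The documents do not support that. SAP 4.8.2 and 6.2.2 count breaks related to adjuvant chemotherapy, or of at most 30 days, as allowed and remove them from the compliance denominator. The Protocol's section on recording AEs also leaves expected chemotherapy side effects out of AE reporting, bleeding excepted. What remains are exits for AEs or medical reasons, other non-compliance and withdrawal. Protocol 10.5 cites a raised bleeding risk with ASA, so exits that differ by arm are conceivable. Nothing shows that they also differ by stage.

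**A reader might infer a sizeable bias in favour of ASA.** For example, with 10% recurrence in stage II and 28% in stage III, and stage III shares of 38% (ASA) and 45% (placebo), the risks are 0.62 × 0.10 + 0.38 × 0.28 = 16.8% and 0.55 × 0.10 + 0.45 × 0.28 = 18.1%, a ratio of 0.93. The arithmetic is right. But if both arms start at 45%, relative stage III retention on ASA must be 1 − (38/62)/(45/55) = 25% lower, with no such loss on placebo. No document supports that, and the opposite direction is equally possible.

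**The analyses carry little weight.** They are exploratory, may be performed, are reported without p-values, and must be presented with their limitations. All of this stands and sets the severity. The caveat about limitations follows from the discussion of censoring weights and does not name stage.

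**Conclusion.** The omission is certain: 15 covariates, stage absent, no reason given, and no outcome model stated for PP3 or PP5. The exact conclusion is that control for stage is not specified, not that it will be absent.

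The consequence is conditional. It needs PP exclusions that differ by both arm and stage. Under the assumptions in the working, gaps of 10 to 20 points in stage III retention move a null hazard ratio by roughly 2 to 10%, up or down. Equal retention moves it by nothing. Against the expected precision the shift is small. The primary and secondary analyses, all on the FAP with the 8.1 strata, are untouched. Severity is minor; the case for acting is that the remedy costs almost nothing.

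**What to change.** In SAP 8.3:

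1. Add pTNM stage (I/II/III) to the denominator model of the stabilised weights, beside tumour location.
2. State that the weighted PP Cox models use the five location-by-stage strata of 8.1. Either change alone removed the shift in the simulation. Stating the strata also closes the gap on the outcome model and keeps the PP and FAP hazard ratios the same kind of quantity. For the combined Mutation A + B analyses in PP5, say whether mutation type joins the strata.
3. Report stage by arm in PP3 and PP5 before and after weighting, so that readers can see whether the issue arose.

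The cost is one model term, one sentence and one small table. No new data are needed. The change should be dated before the treatment code is available for the analysis concerned; if that point has passed for PP3, present it as an added sensitivity analysis and pre-specify it for PP5, whose five-year OS data SAP 5.1 does not expect before August 2026.

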10.1 Table templates

Note that, in the patient characteristics table (Table 14), if there are missing values in a certain variable, a row specifying the number of missing values will be added for that variable.

Table 14. Template for Table 1: Patient characteristics for randomized subjects in the ALASCCA trial.

Characteristic		Randomized to ASA n (%)	Randomized to Placebo n (%)	Mut. group A (ASA) n (%)	Mut. group A (Placebo) n (%)	Mut. group B (ASA) n (%)	Mut. group B (Placebo) n (%)
Age at baseline (years)	Median (IQR, min-max)						
Sex	Female						
	Male						
Country	Sweden						
	Norway						
	Denmark						
	Finland						
Time from CRC surgery to randomization (weeks)	Median (IQR, min-max)						
BMI at baseline (kg/m²)	Median (IQR, min-max)						
Platelet count at baseline (x10^9/L)	Median (IQR, min-max)						
CEA at baseline (µg/L)	Median (IQR, min-max)						
ASA score	1						
	2						
	3						
	4						
	5						
Tumor location	Right colon						
	Left colon						
	Rectum						
Hight from anal verge in rectal	0-5						
cancer (cm)	6-10						
	≥11						
Neoadjuvant treatment in rectal cancer	RT only						
	CRT						
	RT+Chemo						
	CRT+Chemo						
	Chemo only						
	No neoadjuvant treatment						

Statistical Analysis Plan, Version 1.1

Characteristic		Randomized to ASA n (%)	Randomized to Placebo n (%)	Mut. group A (ASA) n (%)	Mut. group A (Placebo) n (%)	Mut. group B (ASA) n (%)	Mut. group B (Placebo) n (%)
Neoadjuvant RT dose (Gy) and	5x5						
fraction in rectal cancer	2x25						
	1.8x28						
	Other						
Surgery	Elective						
	Emergency						
Type of surgery	lleocecal resection						
	Right-sided hemicolectomy						
	Transversum resection						
	Left-sided hemicolectomy						
	Sigmoideum resection						
	Total colectomy						
	Anterior resection						
	Rectum amputation						
	Hartmann's procedure						
	Other procedure						
pTNM stage in colon cancer	ll .						
	III						
pTNM stage in rectal cancer	1						
	II						
	Ш						
Tumor grade	Low grade						
3	High grade						
	Unknown						
MSI	MSI-high						
	MSI-low						
	Uncertain						
BRAF mutation ¹	Yes						
	No						
	Uncertain						
NRAS mutation ²	Yes						
	No						
	Uncertain						

Statistical Analysis Plan, Version 1.1

Characteristic		Randomized to ASA n (%)	Randomized to Placebo n (%)	Mut. group A (ASA) n (%)	Mut. group A (Placebo) n (%)	Mut. group B (ASA) n (%)	Mut. group B (Placebo) n (%)
KRAS mutation ²	Yes						
	No						
	Uncertain						
Adjuvant chemotherapy in colon	Fluorouracil/capecitabin						
cancer	Fluorouracil/capecitabin + oxaliplatin						
	Other adjuvant chemotherapy						
	No adjuvant chemotherapy						
	Missing						
Adjuvant chemotherapy in rectal	Fluorouracil/capecitabin						
cancer	Fluorouracil/capecitabin + oxaliplatin						
	Other adjuvant chemotherapy						
	No adjuvant chemotherapy						
	Missing						

¹V600E ²Exons 12, 13, 59, 61, 117 and/or 146

Table 15. Table template for Table 2: Results from analysis of primary endpoint, and secondary endpoint 1-3. If the PHA is violated, one HR per time-interval (in addition to the overall HR).

Outcome	N (n events) in ASA arm	N (n events) in Placebo arm	HR ASA vs Placebo (95% CI; p)
TTR in PIK3CA exons 9/20			
DFS in PIK3CA exons 9/20			
TTR in PIK3CA (other exons), PIK3R1, PTEN			
DFS in PIK3CA (other exons), PIK3R1, PTEN			

Table 16. Table template for Table 3: Results from analysis of secondary endpoints 4-5.

Outcome	N (n events) in ASA arm	N (n events) in Placebo arm	HR ASA vs Placebo (95% CI; p)
OS in PIK3CA exons 9/20			
OS in PIK3CA (other exons), PIK3R1, PTEN			

Table 17. Table template for Table 4: Results from analysis of exploratory endpoints.

Outcome	Subgroup	N (n events) in ASA arm	N (n events) in Placebo arm	HR ASA vs Placebo (95% CI)
TTR	PIK3CA exons 9/20 (PP3 population)			
TTR	PIK3CA (other exons), PIK3R1, PTEN (PP3 population)			

Table 18. Table template for Table 5: Number of SAEs per randomized arm.

		Randomiz	ed to ASA	Randomized	to Placebo
		Number of SAEs (%)	N subjects in SP	Number of SAEs (%)	N subjects in SP
Total					
Time from randomization (months)	Median (IQR, min- max)				
Type of SAE	Hematological				
• •	Cancer				
	Cardiovascular				
	CNS/Neurological				
	Dermatological				
İ	Endocrine				

		Randomize	Randomized to ASA		to Placebo
		Number of SAEs (%)	N subjects in SP	Number of SAEs (%)	N subjects in SP
	Eyes, ears, nose, throat				
	Gastrointestinal				
	Urogenital				
	Immunological				
	Musculoskeletal				
	Respiratory				
	Other				
SAE description	Leads to death				
	Is life threatening				
	Other important				
	medical event				
	Requires				
	hospitalization for more than 24 hours or				
	extended medical care				
	Causes permanent or significant invalidity/functional				
	impairment				
Intensity	Mild				
•	Moderate				
	Severe				
Treatment modification	Unchanged				
	Stopped				
	Other, e.g. treatment				
	pause				
Result	Restored				
	Under improvement				
	Not Restored, with				
	sequels				
	Death				

Table 19. Table template for Table 6: Number of AEs per randomized arm.

		Randomiz	ed to ASA	Randomized	to Placebo
		Number of AEs (%)	N subjects in SP	Number of AEs (%)	N subjects in SP
Total					
Time from randomization (months)	Median (IQR, min- max)				
Time from start of AE until end of AE (days)	Median (IQR, min- max)				
Type of SAE	Hematological				
• •	Cancer				
	Cardiovascular				
	CNS/Neurological				
	Dermatological				
	Endocrine				

T./22 2272 7222				
Gastrointestinal				
Urogenital				
Hormonal				
Immunological				
Musculoskeletal				
Respiratory				
Other				
Mild				
Moderate				
Severe				
Unchanged				
_				
Stopped				
Other, e.g. treatment				
pause				
Yes				
No				
Yes				
No				
Restored				
Under improvement				
Not Restored, with				
sequels				
Death				
	Hormonal Immunological Musculoskeletal Respiratory Other Mild Moderate Severe Unchanged Stopped Other, e.g. treatment pause Yes No Yes No Restored Under improvement Not Restored, with sequels	throat Gastrointestinal Urogenital Hormonal Immunological Musculoskeletal Respiratory Other Mild Moderate Severe Unchanged Stopped Other, e.g. treatment pause Yes No Yes No Restored Under improvement Not Restored, with sequels	throat Gastrointestinal Urogenital Hormonal Immunological Musculoskeletal Respiratory Other Mild Moderate Severe Unchanged Stopped Other, e.g. treatment pause Yes No Yes No Restored Under improvement Not Restored, with sequels	throat Gastrointestinal Urogenital Hormonal Immunological Musculoskeletal Respiratory Other Mild Moderate Severe Unchanged Stopped Other, e.g. treatment pause Yes No Yes No Restored Under improvement Not Restored, with sequels

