#### 10.13.4 Analysis of safety

AEs will be classified into standardized medical terminology from the verbatim description (Investigator term) using MedDRA. AEs will be presented by preferred term nested within System Organ Class. Verbatim description and all MedDRA level terms, including the lower level terms, for all AEs will be contained in the data listings of the clinical study report for this protocol.

AEs will be summarized by presenting, for treatment group the incidence of AEs. The incidence of AEs will be based on the numbers and percentages of patients with AEs. Although a MedDRA term may be reported more than once for a subject, that subject will be counted only one time in the incidence count for that MedDRA term.

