5.5 Multiple testing

No adjustment for multiple testing will be applied.

6 Summary of trial data

All data will be presented using descriptive statistics, stratified by randomized group and type of somatic alteration. Continuous variables will be summarized using median, interquartile range (IQR), minimum and maximum. Categorical variables will be summarized using the number and percentage of subjects. See Table 14 for a table template of how the baseline variables will be presented.

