The statistical software R (R Foundation for Statistical Computing) will be used, in a version released less than a year before the time of analysis of the primary and secondary endpoints.

10 Listing of tables and figures

Note that the table and figure numbering in the below sections does not necessarily reflect the actual numbering in future publications. Some of the tables and figures may be published separately and in different order. Table formatting, e.g. number of decimals/significant digits, headings, row ordering etc. may be changed to follow the specifications of the selected journal(s).

Table 12. List of tables.

Table	Description	Population	Columns
Table 1.	Patient characteristics for randomized subjects in the ALASCCA trial.	FAP	Randomized to ASA Randomized to Placebo
Table 2.	Results from analysis of primary endpoint, and secondary endpoint 1-3. If the PHA is violated, one HR per time-interval (in addition to the overall HR).	FAP	N per randomized arm, no. of events per randomized arm, HR, 95% CI, p-value
Table 3.	Results from analysis of secondary endpoints 4-5.	FAP	N per randomized arm, no. of events per randomized arm, HR, 95% CI, p-value
Table 4.	Results from analyses of exploratory endpoints.	FAP/PP3	N per randomized arm, no. of events per randomized arm, HR, 95% CI
Table 5.	SAEs per randomized arm.	SP	Number of SAEs per randomized arm
Table 6.	AEs per randomized arm.	SP	Number of AEs per randomized arm
Supplementary Table 1.	Number of AEs per randomized arm and visit, stratified by type of AE.	SP	Number of AEs per randomized arm

Table 13. List of figures. Mutation A: Mutation in PIK3CA exons 9/20, Mutation B: Mutation in PIK3CA (other exons), PIK3R1, PTEN.

Figure	Description	Population	Axis labels (if applicable)
Figure 1.	CONSORT flowchart showing number of screened patients, exclusions, randomized subjects.		
Figure 2a.	CIF curves, with 95% CIs, comparing TTR assessed at 3 years between ASA and Placebo in subjects with somatic alterations in PIK3CA (exons 9/20).	FAP, Mutation A	X-axis "Months from randomization" Y-axis "Cumulative incidence of CRC recurrence (%)"
Figure 2b.	CIF curves, with 95% CIs, comparing TTR assessed at 3 years between ASA and Placebo in subjects with somatic alterations in PIK3CA (other exons), PIK3R1, or PTEN.	FAP, Mutation B	X-axis "Months from randomization" Y-axis "Cumulative incidence of CRC recurrence (%)"

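### The SAP's final safety tables are laid out as SAE and AE counts by broad type with an undefined percentage, and none is laid out for the per-patient MedDRA incidence that protocol 10.13.4 requires

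*SAP*

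**What the plan says.** **Protocol.** Section 10.13.4 presents AEs by preferred term within System Organ Class and fixes the unit: "The incidence of AEs will be based on the numbers and percentages of patients with AEs". For a subject with repeated reports of a term it adds: "that subject will be counted only one time in the incidence count for that MedDRA term". Section 10.8.7.7 has all AEs coded in MedDRA. Section 10.8.5 gives bleeding special attention among the safety assessments.

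**SAP text.** Section 8.2.2 says only that SAEs and AEs in the safety population are listed and summarized by arm. It mentions MedDRA coding for SAEs and is silent on other AEs. Section 6 gives a general rule: "Categorical variables will be summarized using the number and percentage of subjects". The only table it points to is the baseline table.

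**SAP tables.** The template captions are "Table template for Table 5: Number of SAEs per randomized arm" (Table 18) and "Table template for Table 6: Number of AEs per randomized arm" (Table 19). In Table 18 each arm has a column headed "Number of SAEs" with a percentage sign after it, next to a column headed *N subjects in SP*. Table 19 has the same pair for AEs. Rows are broad types such as Hematological, Cardiovascular, CNS/Neurological and Gastrointestinal. Table 12 lists both tables as event counts, and adds Supplementary Table 1: "Number of AEs per randomized arm and visit, stratified by type of AE".

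**The concern.** Frequency and severity of AEs is secondary endpoint 6 in the SAP, so these tables are its planned presentation. The protocol counts patients and the templates count events. The protocol classifies by preferred term, the templates by about a dozen organ groups. A statistician who programs the templates as drawn would not produce the incidence that the protocol specifies, and a reader could not tell whether a printed percentage refers to subjects or to events.

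Bleeding sharpens the point. It is the protocol's stated safety focus, and organ-based types would naturally place a cerebral bleed and a gastric bleed in different rows, each among unrelated events.

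**Working it through.** The plan states no figure to reproduce here. The check is a comparison of texts, followed by two short calculations for scale.

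**1. Unit and classification side by side**

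| Item | Protocol 10.13.4 | SAP Table 12, Tables 18 and 19 |
|---|---|---|
| What is counted | Patients, once per MedDRA term | SAEs or AEs |
| Percentage | Of patients | Denominator not stated |
| Rows | Preferred term within System Organ Class | Broad organ type |

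Other rows also suggest an event unit: both templates have a median time from randomization, and Table 19 has a median time from start to end of the AE. The efficacy templates, by contrast, spell out subjects and events in their headers. The SAP recognizes that events repeat within subjects, because section 7.2 records that the 2020 interim report also summarized subjects with multiple AEs. Table 12 lists no such summary for the final analysis.

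**2. The two readings of *N subjects in SP***

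- *Arm size.* No per-subject count is given, and repeat events in one subject inflate a row.
- *Subjects with the event.* A per-subject count by broad type is available. A stated percentage of patients and the preferred terms are still missing.

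Neither reading gives the protocol's incidence.

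**3. How far the readings of the percentage diverge (assumed counts)**

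Arm size is 300, which is the planned 150 from Group A plus 150 from Group B (protocol 10.7.3). Assume 12 gastrointestinal SAEs, occurring in 4 to 12 patients, among 40 to 100 SAEs in the arm.

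- Events over all SAEs: 12/40 = 30.0%, down to 12/100 = 12.0%.
- Events over subjects: 12/300 = 4.0%.
- Patients over subjects (the protocol's unit): 4/300 = 1.3%, 8/300 = 2.7%, 12/300 = 4.0%.

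Both event-based figures stay fixed as the number of affected patients changes threefold. An events-over-subjects percentage can also pass 100%: an assumed 450 AEs in 300 subjects gives 450/300 = 150%.

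**4. Scale of bleeding**

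Protocol 10.5 puts the increase in gastrointestinal bleeding at around 0.1% per year. Reading this as excess risk, 300 × 3 years × 0.001 = 0.9 expected excess bleeds in the ASA arm. If the drop-outs assumed in protocol 10.1 (10% in Group A, 20% in Group B) contributed no time, 150 × 0.9 + 150 × 0.8 = 255 patients, and 255 × 3 × 0.001 = 0.77. This shows only that events will be few and the output descriptive. It does not measure the effect of the counting unit, because a first bleed in a new patient adds one to a count just as a repeat bleed does.

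**The case against.** The strongest reply is that this is loose labelling. The header is half of a pair: an arm size would be constant down the column and would normally sit in the heading, so *N subjects in SP* can reasonably be read as subjects with that event. The general rule in SAP section 6 is number and percentage of subjects, and it follows a sentence about all data. Nothing in SAP 8.2.2 revokes protocol 10.13.4. The templates may be reformatted for a journal. A clinical trial report (protocol 11.5), reporting in EudraCT and clinicaltrials.gov (SAP 8.2.2) and CONSORT reporting (SAP 4.11) are all planned.

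Much of this stands. It rules out two stronger readings. A reader might infer that the SAP has replaced the protocol's rule, so that patient-based incidence will never appear; the documents do not say so. A reader might also infer that row counts are certainly inflated by repeat events; that holds only if the column is the arm size. What the reply does not supply is a SAP table laid out for the required incidence or a definition of the percentage. The section 6 rule does not match the safety headers, the caveat in section 10 concerns formatting, and the reporting commitments do not state a counting unit.

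On bleeding, a reader might infer that bleeds would go unreported or that a promised table is missing. Neither follows. Cerebral and gastric haemorrhage are named as endpoints for the interim analyses only, and single haemorrhage terms would appear in listings and in the protocol's preferred-term incidence. Two Yes/No row pairs in the available text of Table 19 have lost their labels, so the absence of a bleeding row is certain only for Table 12 and the readable template rows.

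The SAP's silence on MedDRA coding of non-serious AEs is not a contradiction either, since protocol 10.8.7.7 covers them.

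**Conclusion.** The concern holds as a mismatch between the analysis unit in protocol 10.13.4 and the layout of the SAP's safety tables. Confidence is high that the percentage is undefined and that no SAP table is laid out by patient and preferred term; both follow from the text and need no assumption. Whether rows are also inflated depends on the unstated role of one column. The percentages in the illustration rest on assumed counts and show ambiguity, not a predicted error.

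The consequence is limited to descriptive safety output. It is worth correcting because it concerns a listed secondary endpoint and a rule that the protocol already sets. The missing bleeding row is a separate matter: a cheap improvement, not an error.

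**What to change.** **Correction.**

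- In Tables 18 and 19 and Supplementary Table 1, report subjects with at least one event as n (% of the safety population in that arm).
- Keep event counts in a separate, labelled column, and define *N subjects in SP*.
- State in SAP 8.2.2 that incidence follows protocol 10.13.4, by preferred term within System Organ Class, with all AEs MedDRA-coded as protocol 10.8.7.7 requires.
- Bring the column descriptions in Table 12 into line.

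**Optional improvement.** Add a subject-level bleeding row per arm (any, cerebral, gastric or other gastrointestinal), labelled descriptive, from a MedDRA term list fixed before unblinding. Protocol 10.13.4 fixes the counting unit but not which terms together count as bleeding.

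**Cost.** Edits to SAP 8.2.2, Table 12 and the two templates, some reprogramming, and a short term list if the bleeding row is adopted. No new data are needed: protocol 10.8.7.2 already has all AEs recorded, apart from expected chemotherapy side effects and enterostomy-closure complications, and bleeding linked to those is still reported. If non-serious AEs have not yet been coded, that is real work, but the protocol already requires it. The efficacy analyses and the completed interim reports are unaffected.
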